For the CloseST study, we will aim to recruit up 210 study participants in the C-STRAND trial diagnosed with COVID-19. Data from the Philadelphia Department of Public Health shows that the median number of close contacts provided per individual with COVID-19 is approximately three.²¹ Assuming the mean number of close contacts *infected* with COVID-19 is approximately one, and 50% obtain testing, we can expect the mean number of positive tests per index COVID-19 positive index participant to therefore be approximately 0.5. We assumed a conservative allocation ratio of 2:1 and estimated the standard deviation of the number of positive tests in the network of COVID-19 positive index participants to be between 0.6 and 0.8. We considered a doubling from 0.5 to 1.0 new cases identified per positive index to be clinically significant. At the low end of the standard deviation range, we would need a total N=54 for 80% power with a p=0.05. With a standard deviation as high as 1.0, we would need a total N=192 to have 90% power to detect a difference between groups. A total of 210 individuals (representing a 20% positivity rate among Index Participants), even with a standard deviation of 1.0, would give us 93% power to detect a doubling of positive cases identified.

Data Analysis

All analyses will be performed based on intention-to-treat. In the C-STRAND trial, the primary analysis will use the Cochran-Mantel-Haenszel test, adjusting for study site, to compare the proportion of individuals in each arm who succeeded in getting two contacts tested. Sex will be included with an interaction term in multivariable models using logistic regression. In secondary analyses, Wilcoxon Rank-sum tests and linear regression or negative binomial regression will be used to compare each of the count and continuous outcomes (e.g., total number of contacts tested).

In the CloseST study, we will use Poisson regression to compare the number of contacts who test positive at week 8 among contacts of SARS-COV-2 positive individuals who received the intervention or the control. Additional comparisons will follow the same approach for the secondary outcomes. Standardized mean differences (SMDs) > 0.1 will be used to determine balance between arms and identify potential confounders between participants in either study arm. If there is imbalance in the characteristics between the arms, additional analyses will consider potential confounders, including age, race/ethnicity, education, employment status, socioeconomic status, housing status, household size, relationship status, risk of COVID-19 exposure, and site of recruitment.

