In order to link Network Contacts who obtain COVID-19 tests to Index Participants, each Index Participant will be assigned a Referral Identification (ID) number. This number will appear on all test referral cards and text messages in the control group, and on test kits in the intervention group. When network contacts request testing, they will be asked to provide the Referral ID number linking them to the Index Participant. We will measure test uptake among self-testers through testing completed at the partner self-testing lab. Among facility-based testers, test uptake will be measured through testing at one of the clinic sites. Study personnel will communicate all test results back to study participants via telephone, with an electronic copy of test results available upon request.

Outcomes

The primary outcome in the C-STRAND trial is the proportion of Index study participants linked to at least two Network Contacts who completed testing. Secondary outcomes at the end of the follow-up (week 8) and end of the study by each arm include: number of contacts tested, number of network contacts who test positive, test positivity rate and proportion of first-time test takers. All of these outcomes will be assessed with collected testing results and not rely on self-reported measures. Baseline and follow-up surveys will provide self-reported outcomes related to socio-demographic characteristics as well as COVID-19 exposure, symptoms, testing, and vaccine acceptance.

For the CloseST study, the primary outcome is the number of close contacts who test positive in each group.

Secondary outcomes at the end of the follow-up (week 8) by each group, include number of contacts tested and number of new cases identified. Similarly, baseline surveys of network contacts in the cohort study will provide similar self-reported outcomes as in aim 1.

[figure not shown]
INDEX PARTICIPANTS

Index participants are the study participants that we are enrolling in our primary study. They are adults who are seeking care at one of the three PHMC sites, and we are aiming to recruit them to then distribute home test kits or clinic test referrals to their contacts.

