We will recruit Index Participants both A) Over the phone, by calling patients scheduled for COVID testing prior to their appointment, and B), In-person, for individuals over 18 either receiving COVID testing at participating clinic sites (“testers”) or coming in for other medical appointments (“non-testers”). See Figure 2 below.

In September 2021, we expanded eligibility to no longer require COVID-19 testing to be enrolled in the study. People who are not getting tested for COVID-19 are eligible to join the study if they are already registered patients in the PHMC clinic network who go to a PHMC clinic for any type of appointment and contact a study Interviewer to ask about the study. Flyers with basic study information and contact phone numbers on them have been printed out and placed in the clinics where patients can see them.

Figure 2: Study flow for Index Participants recruited over the phone and in-person

Index participants recruited over the phone

Steps 1-2: Recruitment, Eligibility assessment, and Enrollment of Index Participants:

As outlined in Figure 2 above, we will recruit over the phone and in-person.

In-person recruitment:

Study staff will offer recruitment in-person to testers. At that point, COVID-19 testing should be completed already.

Non-testers interested in joining the study after reading a study flyer will contact study staff.

At Rising Sun, the Interviewer will also actively recruit COVID vaccine patients and patients who are new to the clinic.

Eligibility Assessment

Who: CSTRAND research Interviewers

For participants recruited over the phone, interviewers are responsible for calling individuals scheduled to be tested for COVID-19 at their specific site (Health Connection, Rising Sun, or Care Clinic).

For participants recruited in person, Interviewers are responsible for approaching individuals being tested for COVID-19 directly to assess eligibility. Interested non-testers will contact Interviewers about the study.

What: Interviewers will call or talk with individuals who expressed interest assess eligibility.

When: During Step 1 Initial Recruitment

For Phone only:

1. Research Interviewers are responsible for monitoring their respective clinics' COVID-19 testing schedules to identify prospective participants.

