For network contacts:

If Network Contacts test positive and enroll in the CloseST study, their REDCap ID number will become their “Referral ID number.” Their ID numbers will start with 1 and go up after that.

Study intervention:

Self-test kit arm procedures:

If randomized the self-test kit arm, the interviewer will go through script C “Index Participant randomized to self-test kit.”

The interviewer will retrieve a package of 5 self-test kits. Self-test kits will be kept in secure locations determined by the staff of the participating clinic sites.

Assigning test kits to the index participant:

- The interviewer will affix a sticker to each of the 5 test kits instructing them to download the Ellume app. It will also include a QR code for network contacts to scan with a smartphone and a URL that network contacts can type into a web browser on a smartphone. The QR code or link will send the network contact to a page on the Ellume app for them to have their test sample analyzed. All 5 test kits will have the same

QR code and URL. For the purposes of this study, the PIs have bought the domain name *testphilly.com*. Each URL that will accompany a QR code on a test kit will include a number. The numbers will start with 1, and go up sequentially (for example, *testphilly.com/1*, *testphilly.com/2*, *testphilly.com/3*, etc.). All 5 test kits given to the same index participant will have the same QR code and URL on them.

- Each test kit will have instructions on downloading the app, taking a sample using the test kit, and having the sample analyzed, attached to it with a rubber band.

Post-randomization assessment

The Interviewer will also ask the Index Participant the “Intentions” instrument.

Self-testing kits:

The Interviewer will provide an explanation to the index participant of how to distribute test kits to contacts and how to use test kits.

In order to use the test kits, a network contact will need to have a smartphone with Bluetooth capability, and they will have to download the Ellume app. and then go to the URL on the test kit or scan the QR code.

Index participants can give the test kit to anyone aged 2 or older.

Intervention instructions:

Participants will be encouraged to distribute the self-tests to individuals in their social network, including family members, with encouragement to deliver to network contacts ages 2 and older who:

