Individuals in the test-referral arm must meet the following eligibility criteria:

1. At least 2 years of age
2. Have access to a working phone number
3. Able and willing to provide informed consent if 18+
4. Able and willing to provide assent and parental permission if ages 2-17.

Exclusion criteria

5. Severe symptoms requiring urgent medical attention
6. Not meeting any of the above inclusion criteria

Verbal informed Consent and clinic test registration:

Network contacts will be given referral cards or text messages to call in to get tested.

The phone number will be linked to the PHMC clinic site through which they are referred. The interviewer will then assist the network contact with informed consent and test registration.

See Study Script F “**Verbal Consent – Network Contact TR**”

1. If the individual declines consent, the interviewer will only mark that a phone call was made to schedule a test but will not retain the test referral number or any PHI.
2. If the individual provides verbal consent to participate in the study, the interviewer will record the individual’s scheduled test and their name into the database to be tracked.

Electronic consent or in-person signed consent:

3. Individuals will have the option for electronically consenting for the study prior to arriving at PHMC clinic sites if desired.
4. If electronic consent forms are requested, they can be found at:
 - i. Redcap.link/cstrandadult (ages 18+)
 - ii. Redcap.link/cstrandteen (ages 12-17)
 - iii. Redcap.lilnk/cstrandchild (ages 2-11)
5. A PDF copy of the electronic consent form will be downloadable after signing

If the Network Contact declines consent, the interviewer will only mark that a phone call was made to schedule a test but will not retain the test referral number or any PHI. If the Network Contact provides verbal consent to have the number and PHI retained, the interviewer will record the patient’s scheduled test in the research database. Only the patient’s medical record number and test referral number will be included in research database for test tracking purposes. The research interviewer will then track the test referral to see if the Network Contact completed testing.

Signed informed consent, clinic testing, and study compensation

Interviewers will approach Network Contacts when they arrive for their scheduled testing.

1. Interviewers will confirm that Network Contacts have signed informed consent electronically

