- The interviewer will ask individuals about close contacts
- The interviewer will elicit close contact information, and help the individual prioritize who to give testing to.
- The interviewer will instruct COVID-19 participant to tell close contacts to quarantine, monitor symptoms, and that if desired, they can obtain testing at PHMC clinics
- The interviewer will then send the COVID-19 participant a “COVID-19 referral text” (See Script N.3 “[Text message for COVID-19 positive contact test referral](#)”) that they can forward to contacts.

Network contacts in self-test kit arm who test positive:

- Need to be registered in RedCap

Study compensation:

Index Participants:

- At the end of the phone call, the interviewer will ask the COVID+ participant if they still have their ClinCard.
 - If they have their ClinCard, this will be reloaded with \$15.
 - If they do not have their ClinCard, they can be sent a \$15 compensation through an electronic gift card (Target gift card or electronic ClinCard, if available).

Network Contacts

- Study compensation for network contacts who enroll in COVID+ cohort:
 - They will be able to receive **\$30** as target virtual gift cards as a single one-time payment.

Sample Size

The sample size for the C-STRAND trial was calculated based on the primary outcome of Aim 1. Power calculations were completed using STATA 15.1 (STATA Corp, College Station, TX). With an estimate that 45% in the control group achieve success, defined as at least two network contacts completing testing, we calculated a sample size of 1048 needed to detect a 10% difference (two-tailed alpha of 0.05, power of 90%). If in fact we observe a success rate as low as 25% in the control group, with a sample size of 1048, we will have 90% power to detect as small as an 8% difference.

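### For the app-read kits, no described step separates an index participant's own result from a contact's, so it can count toward the two-contact primary outcome in the kit arm, while the referral arm records enough to detect it

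*Combined protocol and SAP*

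**What the plan says.** The Overview of study defines Network Contacts as people who receive kits or referrals from an index participant. Outcomes defines success as "the proportion of Index study participants linked to at least two Network Contacts who completed testing", and says that outcomes come from collected test results and not from self-report.

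**Kit arm, app-read kits (from December 2021).**
- Assigning test kits to the index participant: "All 5 test kits given to the same index participant will have the same QR code and URL on them".
- Index Referral ID Number: numbers of the app-read kits are not tracked.
- Self-test arm, under Network Contacts: exclusion criteria are none, consent is waived, and registration is done in the vendor's app.
- Self-Collection Test Kits, December 2021 update: a result reaches the study portal if the QR code was used.
- Self-testing kits: "Index participants can give the test kit to anyone aged 2 or older". Staff also explain to the index participant how the kits are used.

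**Referral arm.** The caller gives the referral number and verbal consent, the name is recorded, and the "medical record number and test referral number will be included in research database for test tracking purposes". An interviewer meets the person at the clinic.

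**Both arms.** Since September 2021, "we expanded eligibility to no longer require COVID-19 testing to be enrolled in the study".

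**Passages that do not agree.** The Overview says self-testers' results can no longer be monitored after the switch, whereas the December 2021 update describes a portal that receives them. Registration of test kits still requires consent, name, date of birth and phone number, whereas the later self-test section waives consent and moves registration to the app.

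**The concern.** The only described link for an app-read kit runs from the kit to the index participant who was handed it. A result from the index participant's own nose and a result from a contact would arrive under the same URL. Own use is plausible: people who were not tested at enrolment can join, and they leave with five kits and an explanation of how to use them.

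The threshold is two. If an own test is counted, one real contact is enough for success in the kit arm, while the referral arm still needs two. The number of contacts tested and the number testing positive would be affected in the same way.

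Counting distinct persons would not solve this, because the index participant is one distinct person. Nor could an analyst repair it afterwards unless something that identifies the index participant had been captured.

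**Working it through.** **Inputs from Sample Size:** control success 45%, two-sided 5% significance and 90% power, for which the section states "we calculated a sample size of 1048 needed to detect a 10% difference". Allocation is 1:1 (Trial Design), with five kits or cards each (Intervention, Control).

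**Step 1. Reproduce the plan's figure.** Per arm, n = [1.960·√(2·0.5·0.5) + 1.2816·√(0.45·0.55 + 0.55·0.45)]² / 0.10² = (1.386 + 0.902)² / 0.01 = 523.3, so 524 per arm and 1048 in total. The stated sample size reproduces.

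**Step 2. Model with no true arm difference.** Let X be the number of contacts tested when all five are passed on, with P(X ≥ 2) = 0.45 in both arms.
- Independent use: X ~ Binomial(5, p) gives p = 0.289.
- Correlated use: beta-binomial with within-index correlation 0.3 gives p = 0.322.

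**Step 3. One own test counted.** Four kits remain and one real contact is enough.
- Independent: P(at least 1 of 4) = 1 − (1 − 0.289)⁴ = 0.745, which is 29.5 points above 45%.
- Correlated: P(at least 1 of 4) = 0.627, which is 17.7 points above 45%.

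The count changes the result only for index participants with exactly one real contact tested.

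**Step 4. Apparent kit-arm rate.** If a share s of the whole kit arm does this, the rate is 0.45 + s·0.295 (independent) or 0.45 + s·0.177 (correlated). The chance of a significant result uses the two-sided 5% two-proportion test at 524 per arm, ignoring site strata.

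| s (assumed) | Independent: gain | Significant | Correlated: gain | Significant |
|---|---|---|---|---|
| 10% | +3.0 points | 16% | +1.8 points | 9% |
| 20% | +5.9 points | 48% | +3.5 points | 21% |
| 30% | +8.9 points | 82% | +5.3 points | 41% |

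Here s is the app-period share of enrolment times the self-use share within that period. The documents give neither. If half of the kit arm enrolled in that period and 20% of those self-used, s would be 10%.

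**Step 5. Opposing error.** Suppose a share u of kit tests never reaches the portal because the QR code was not used. With q = 0.289·(1 − u), the rate is (1 − s)·P(Bin(5,q) ≥ 2) + s·[(1 − u)·P(Bin(4,q) ≥ 1) + u·P(Bin(4,q) ≥ 2)].
- u = 5%, s = 10%: 0.9·0.420 + 0.1·(0.95·0.724 + 0.05·0.305) = 0.448, a net −0.2 points.
- u = 10%, s = 20%: net −0.7 points.
- u = 10%, s = 10%: net −3.4 points.
- u = 5%, s = 30%: net +5.5 points.

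The sign depends on two unmeasured rates.

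**Step 6. Check a blunt correction.** Suppose three results were required of every kit-arm participant. A true 55% rate (p = 0.339) becomes P(Bin(5, 0.339) ≥ 3) = 22%, or 37% with correlation 0.3, against 45% in control. A real 10-point benefit would be reversed.

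**The case against.** The strongest reply is that the definition of a Network Contact already excludes the index participant, so only an enforcement step is missing, and that the documents report no self-use. That stands. The point concerns what the plan lets through, not something shown to have happened.

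Four further objections have force.
- **Referral arm.** A reader might infer that own use cannot happen there. The documents do not support this. The referral-arm exclusions do not name the index participant, and untested index participants exist in both arms. Own use of a card is detectable there, not impossible, and no rule removes it.
- **Identifiers.** Registration of test kits requires name, date of birth and phone number and is not marked as superseded. If it applies to the app-read kits and the data reach the study, matching is possible. The later move to app registration leaves this unclear, and no passage says that matching will be done.
- **Unseen material.** The script for kit-arm participants and the week-8 survey instrument are not in the available text and may already address own use. Even so, the outcome definition and analysis sections contain no rule that uses such information.
- **The sentence on giving kits to anyone aged 2 or older** concerns giving kits to others. It does not itself permit own use. The shared QR code, untracked kits and waived consent carry the argument.

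**Conclusion.** The gap is real and differs by arm. As written, an app-read result from the index participant can enter the primary count as a contact's, and no described step would detect it, whereas the referral arm records name and medical record number. The possible gain is about 3.0 to 8.9 points (independent use) or 1.8 to 5.3 points (correlation 0.3) at 10% to 30% self-use over the whole kit arm, against a design difference of 10 points. The self-use rates and contact distributions are assumptions, and the app-period share of enrolment is unknown.

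A reader might conclude that the primary outcome is inflated in favour of the kits. The documents do not support that. They show a route and no occurrence, and unused QR codes lower the kit-arm rate. Two unmeasured errors in opposite directions do not validate the outcome, however, and each needs its own check. The point should be addressed before the primary analysis; the sample size of 1048 is not affected.

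**What to change.** 1. In Outcomes, state that only tests taken by persons other than the index participant count toward any Network Contact outcome, in both arms.
2. On the study-owned URL, before the app opens, add one yes/no item: *Are you the person the study gave these kits to?* Alternatively, match portal identity to the index record, if the portal supplies identity.
3. In the week-8 index survey, ask how many of the five the index participant used personally and, for kits, whether the QR code was used.
4. In Data Analysis, pre-specify a sensitivity analysis of the primary outcome that removes self-used, QR-linked results. Use the survey answers only there, because Outcomes rules out self-report.
5. For participants already enrolled without these items, report the primary comparison over a range of assumed self-use shares. Show the three-result requirement only as an extreme bound, since it can reverse a true benefit.
6. Reconcile the Overview (self-test results no longer monitored), the December 2021 update (results reported to a portal), Registration of test kits (consent, name, date of birth, phone) and the self-test arm section (consent waived, app registration), and state which identifiers the study receives.

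The cost is one extra tap before the app opens, two short survey items and a few sentences of text. The kit-arm rate may come out lower.
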